5.7.3 Reduction of bias: blinding of test interpretations

- Index test interpretations (ctDNA/ other biomarkers) will be blinded from other index tests (RMI, CA125, USG). Some of the index tests in current pathways will be interpreted as part of current practice and blinding between these test interpretations will be maximized whilst maintaining patient best care.
- Index test interpretations will be blinded where possible from rest of diagnostic pathway – i.e. only using relevant clinical information known at time in clinical pathway.
- Index test interpretations will be blinded from reference standard interpretation (histology and clinical follow up).
- As part of the blinding, the analysis algorithm for ctDNA from plasma will be analysed using auditable analysis code which will be locked down prior to comparison to surgical tumour mutation comparison.

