1.6. Other novel markers

Currently there is multiple promising biomarkers for early cancer detection including circulating tumor DNA (ctDNA)^{24,30,31}, microRNAs (miRNAs)³⁹, cancer glycomics^{48,49,50} and protein biomarkers^{40,41,44-46}, with emerging research exploring metabolites^{42,47} and epigenetic markers like DNA methylation⁴³. In ROCKeTS GEN V2, based on our developing understanding of technologies, we will analyse samples collected with some/all these technologies to try and identify the best biomarkers for OC.

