In ROCKeTS GEN V2, the index tests (ctDNA analysis) will be externally validated at the end of the study. Therefore, we will collect dried blood spots, serum and plasma in the study to be analysed and validated at the end of the study.

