2.6 Analysis

Plasma ctDNA analysis at Cancer Molecular Diagnostic Laboratory (CMDL) will be performed blind from tissue DNA analysis. Sensitivity and specificity of plasma ctDNA will be established by statistical analysis. Blood and dried blood spot samples will be stored and analysed for multiple analytes such as proteins, by CMDL and QMUL. The genomic methodology will be used, including whole genome sequencing. ROCKeTS-GEN v2 uses a rapidly changing technology for analysis and therefore exact detail on how the analysis will be performed will not be detailed in the protocol but will be detailed in full in the final report and any publications.

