2.10 Schedule of Events & CRF completion for ROCKETS-GEN V2

Table 1: Schedule of events and CRF completion

	Screening	Baseline	≤ 12 months
Eligibility Check	x ¹		
Valid Informed Consent	x ¹		
Registration Form CRF		x	
Online registration		x ²	
GP Letter		x	

Blood sample		x ⁴	
IOTA USG		Optional	
Ultrasound CRF		Optional	
Participant Baseline CRF		x ³	
Surgery CRF			Post-surgery/biopsy
Representative tissue block/s			x ⁵
Outcome CRF			12 months – only required if histology/cytology not obtained

¹ See section 'Approaching Potential Participants to Consent'.

² It is acceptable to delay registration until blood sample, IOTA USG & Participant Baseline CRF are complete.

³ Blood sample, IOTA USG and Participant Baseline CRF should all be captured within 3 months of whichever of the following occurred first: presentation, IOTA USG (see section 5.1).

⁴ Blood samples including dried blood spots, serum and plasma, send immediately to CMDL

⁵ Tissue sample (if participant proceeds to surgery) or biopsy send to Central study lab (CMDL or QMUL).

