7.4.1 Data sharing

There are data sharing agreements in place between the CMDL, Barts groups and with the ROCKETS Trial Team. Over the duration of the study data, will be shared between these groups. All data shared between groups will be fully anonymised and has been clearly explained in the PIS and consent form.

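### Blinding is stated, but the ctDNA classifier and its positivity cut-off are not locked before the reference-standard comparison that yields the accuracy estimates

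*Protocol*

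**What the plan says.** **Type of evaluation.** Section 2.2 states that "the index tests (ctDNA analysis) will be externally validated at the end of the study". Section 5.7.1 relates every test comparison to the reference test. Section 2.2 defines that reference as histology or cytology or, without surgery or biopsy, the 12-month outcome.

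**Index test.** The primary outcome in 5.7.2 names only ctDNA. Section 1.5 describes TP53 mutation, copy number, fragmentomics and methylation as sources of signal. Section 1.6 says that "we will analyse samples collected with some/all these technologies to try and identify the best biomarkers for OC". Section 2.6 says that "exact detail on how the analysis will be performed will not be detailed in the protocol" and names the final report and publications as the place for it.

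**Lock.** The last bullet of 5.7.3 requires analysis code that can be audited and "which will be locked down prior to comparison to surgical tumour mutation comparison". It mentions no cut-off.

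**Blinding.** Section 2.6 keeps plasma analysis blind to the tissue DNA work. Section 2.8 blinds the CMDL and QMUL teams to the clinical dataset, which stays at the University of Birmingham. The laboratories send their results there, and they are then checked against outcome. The third bullet of 5.7.3 blinds index-test interpretation from the reference standard.

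**Flow of material.** Under Table 1 (section 2.10), blood goes to CMDL and tissue to CMDL or QMUL. Section 7.4.1 adds: "Over the duration of the study data, will be shared between these groups".

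**The concern.** External validation means that a test fixed beforehand is applied unchanged to new patients. Here the protocol names no single ctDNA test and no cut-off, and the one lock it sets does not guard the comparison that produces the primary result. Comparing plasma calls with tumour mutations verifies the origin of the signal. It does not give sensitivity or specificity for ovarian cancer.

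Blinding each plasma call does not solve this. A laboratory could make honest, blinded calls on several platforms or at several cut-offs, send them all to Birmingham, and the best performer could then be reported as the ctDNA result. Every blinding statement would have been respected. The reported sensitivity would still be too high, because selection and estimation used the same women. RMI 1 is an established score with a numeric cut-off and would gain nothing comparable. (Sections 2.5 and 5.7.2 give that cut-off as 200 and 250, which is a separate matter.) The bias would fall on the primary comparison and always in favour of ctDNA.

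**Working it through.** **1. Does any stated step fix the index test before accuracy is calculated?**

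| Step | Where | What it secures |
|---|---|---|
| Plasma blind to tissue DNA analysis | 2.6 | The individual plasma call |
| Laboratories blind to clinical dataset; results sent, then checked | 2.8 | The individual plasma call, and the order of submission and check |
| Index interpretation blind to reference standard | 5.7.3, third bullet | The individual plasma call |
| Code lock | 5.7.3, last bullet | Code, but only before the tumour-mutation comparison |

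None of the four names one primary classifier, fixes a cut-off, or says that a single set of results is submitted once and frozen. Read literally, code revised after comparison with histology but before comparison with tumour mutations would comply.

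**2. How many women carry the primary sensitivity estimate?** Inputs are from 5.7.2.

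- Analysed: 500 × 0.95 × (1 − 0.145) = 406.1. This reproduces the plan's 406 near the upper end of its 10-15% without surgery or biopsy (10% gives 427.5, 15% gives 403.8).
- Ovarian cancers: 406 × 0.27 = 109.6, the plan's 110.
- HGSOC: 110 × 0.70 = 77. Early stage: 77 × 0.25 = 19.25, so about 19.

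**3. How large could selection be?** The number of tests k, the true sensitivity p and the correlation between tests are assumptions; the documents give none of them. For k equally good tests, expected inflation is roughly E(k) × √(p(1 − p)/19). E(k) is the expected maximum of k standard normals: 0.56 for k = 2 and 1.03 for k = 4 if independent, 0.40 and 0.73 at correlation 0.5.

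- Standard error: √(0.25/19) = 0.115 at p = 0.5; √(0.21/19) = 0.105 at p = 0.7.
- k = 2: from 0.40 × 0.105 = 0.042 to 0.56 × 0.115 = 0.064, about 4 to 6 points.
- k = 4: from 0.73 × 0.105 = 0.077 to 1.03 × 0.115 = 0.118, about 8 to 12 points.

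An exact binomial calculation for two independent tests on 19 cases agrees: 50% becomes 56.4%, and 70% becomes 75.9%.

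**4. If selection used all 110 cancers**, with equal sensitivity across them, the inflation shrinks by √(19/110) = 0.42, to about 2 to 3 points for k = 2 and 3 to 5 points for k = 4.

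**5. Does the arrival of a tissue block disclose cancer?** Of 475 women followed (500 × 0.95), about 406 would have surgery or biopsy. If all 110 cancers were among them, a block would move the probability of cancer from 110/475 = 23% to 110/406 = 27%. That says little.

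**The case against.** The strongest defence is that the protocol builds a real firewall. Outcomes stay in Birmingham, samples carry study numbers only, and section 2.8 has results sent before they are checked against outcome. The code lock is introduced as one part of the blinding, not as the whole of it. The candidate signals appear in background text, and the search for the best biomarkers stands under other novel markers. Section 1.5 reports an existing methylation classifier that was already assessed blindly. A classifier version and cut-off often sit in a statistical analysis plan, which is not at hand.

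Much of this stands, and it rules out several stronger readings:

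- A reader might infer that the validation is unprotected or unblinded. Sections 2.6, 2.8 and 5.7.3 say otherwise.
- A reader might infer that holding a block reveals reference status to those making plasma calls. On the plan's own figures (step 5) receipt alone is barely informative. Tissue staff may learn more, since section 2.2 has DNA extracted from cancer tissue after pathology review, but 2.6 blinds plasma analysis from that work. How staff are separated may be described in the laboratory manual.
- A reader might take 7.4.1 to release outcomes to the laboratories. It does not say so, it requires anonymised data, and 2.8 blinds the laboratories to the clinical dataset. Anonymised is not the same as blinded, however, and 7.4.1 does not exclude outcome data.

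What the defence does not answer is selection among tests. The order in 2.8 protects each call, not the choice of which calls count. Nor can the gap be left to an unseen plan: 2.6 itself points to the final report and publications, and 5.7.3 itself states the lock point.

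**Conclusion.** The point holds as a gap in pre-specification, not as a failure of blinding. The stated lock precedes the tumour-mutation comparison instead of the reference-standard comparison, no cut-off is locked, and the ctDNA method may stay open until the report of a study described as external validation. Choosing the best of several ctDNA tests would comply with the text and would favour ctDNA over RMI 1.

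The size is illustrative: about 4 to 12 points of sensitivity for the best of 2 to 4 tests selected on about 19 early-stage HGSOC cases, or about 2 to 5 points if selection used all 110 cancers. Both ranges assume true sensitivity of 50-70%, correlation of 0 to 0.5, equally good tests, and a choice made after outcomes are seen. The documents do not say that such a choice is intended. The correction should be made before any comparison with outcome.

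**What to change.** Reword 5.7.3 so that one named primary ctDNA classifier, its code and a single positivity cut-off are locked and lodged with the University of Birmingham, together with the plasma calls for all participants. This must happen before any comparison with histology, cytology or 12-month outcome, and before those making the plasma calls see tissue results. State that all other platforms, signals and cut-offs are exploratory, and bring 1.6 and 2.6 into line.

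In 7.4.1, state that outcome and tissue results are not shared with the plasma analysts before that lock. Other sharing can continue. Blocks need not be held at sites: they may go to CMDL or QMUL as planned if they are kept from the plasma analysts, for example under separate coding.

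The cost is wording and a dated deposit. The one small downside is that the technology cannot be changed after the lock for the primary analysis; it can be updated freely until then.

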6 ADVERSE EVENT REPORTING

There are no foreseeable risks of mortality or significant morbidity associated with testing. Every effort will be made to minimise any risk through training. **Therefore, only serious adverse events* (SAEs) believed to be associated with any study procedures should be reported.** SAEs should be reported via email to the study email address.

The collection and reporting Serious Adverse Events (SAEs) will be in accordance with Good Clinical Practice (GCP) and the Research Governance Framework 2005.

Safety will be assessed continuously throughout the study. There are no Investigational Medicinal Products being used as part of the ROCKETTS-GEN V2 study and the tests evaluated in the study are not being used to determine patient management. A risk assessment of the ROCKETTS GEN V2 study has been performed with all testing considered to be of low risk.

6.1 Definition of a Serious Adverse Event

The definition of an SAE is an untoward event that:

- results in death
- is life-threatening*

*For the purposes of this study, “serious” adverse events are those occurring in participants which are fatal, life-threatening, disabling or require some form of medical or surgical treatment.

- requires hospitalisation** or prolongation of existing hospitalisation
- results in persistent or significant disability or incapacity
- Consists of a congenital anomaly/ birth defect
- or, is otherwise considered medically significant by the Investigator

*The term “life-threatening” refers to an event in which the patient was at risk of death at the time of the event; it does not refer to an event which hypothetically might have caused death if it were more severe.

** Patients must be formally admitted – waiting in out-patients or A&E does not constitute an SAE (even though this can sometimes be overnight). Similarly, planned hospitalisations that clearly are not related to the condition under investigation or hospitalisations/prolongation of hospitalisation due to social reasons should not be considered as SAEs.

6.2 Reporting period

The main theoretically possible recognised reportable SAEs associated with this study relate to the dried blood spot, serum and plasma sample being taken, USG conducted or distress following answering questions in baseline CRF.sSAEs occurring within 24 hours of one of these events should be reported immediately upon awareness to the study office on an SAE form. The assessment of relatedness and expectedness is a clinical decision based on all available information at the time.

SAEs outside of this timeframe can also be reported if it is the opinion of the Investigator that there is a possible causal relationship to another aspect of the study. An assessment of relatedness and expectedness will also be undertaken by the Chief Investigator (or designee).

6.3 Reporting procedure – at Site

SAEs believed associated with any study procedures will be notifiable to Study Office **immediately and within 24 hours of becoming aware of the event**. On becoming aware that a participant has experienced said SAE, the Investigator (or delegate) must complete, date and sign an SAE Form. The form should be sent to Study Office using the study email address. The Investigator will also be asked to provide a categorisation of seriousness and causality (continue reading for further details).

For contact details, refer to the ‘ROCKeTS GEN V2 Study Office’ section at the front of this protocol.

For SAE Forms completed by a member of the site trial team other than the Principal Investigator (PI), the PI will be required to countersign the original SAE Form to confirm agreement with the causality and seriousness/severity assessments. The form should then be returned to Study Office and a copy kept in the Site File.

Investigators should also report SAEs to their own Trust in accordance with local practice.

6.4 Causality assessment

AEs defined as serious, and which require reporting as an SAE should be reported on an SAE Form. When completing the form, the PI (or delegate) will be asked to define the causality and the severity of the AE.

Causality (relatedness) will be categorised according to the following Table 2.

Table 2: Definitions of relatedness

Category	Definition	Causality
Definitely	There is clear evidence to suggest a causal relationship, and other possible contributing factors can be ruled out	Related
Probably	There is evidence to suggest a causal relationship, and the influence of other factors is unlikely	
Possibly	There is some evidence to suggest a causal relationship. However, the influence of other factors may have contributed to the event (e.g. the patient's clinical condition, other concomitant events or medication)	
Unlikely	There is little evidence to suggest there is a causal relationship. There is another reasonable explanation for the event (e.g. the patient's clinical condition, other concomitant events or medication)	Unrelated
Unrelated	There is no evidence of any causal relationship	

6.5 Assessment of Expectedness

Expectedness will be assessed by the CI or designee using this study protocol as the reference document. Table 3 gives definitions of expectedness with respect to SAEs.

Table 3: Definitions of expectedness

Category	Definition
Expected	An adverse event that is consistent with known information about the study related procedures.
Unexpected	An adverse event that is not consistent with known information about the study related procedures

6.6 Provision of follow-up information

Participants should be followed up until resolution or stabilisation of the event. Follow-up information should be provided on a new SAE Form, making sure to include the SAE reference number, provided by the Trials Unit upon receipt of the initial SAE.

6.7 Reporting procedure – ROCKeTS GEN V2 Study Office

On receipt the Study Office will allocate each SAE a unique reference number which will be forwarded to the site as proof of receipt within 1 working day. The SAE reference number will be quoted on all correspondence and follow-up reports regarding the SAE.

On receipt of an SAE Form, seriousness and causality (relatedness to the study intervention) will be assessed independently by the CI. Further information may be immediately requested from the clinical team at site. The CI will not overrule the causality or seriousness assessment given by the site PI but may add additional comment on these.

An SAE judged to have a reasonable causal relationship with study processes will be regarded as a related SAE. The CI or delegate will assess all related SAEs for expectedness. If the event is assessed as unexpected it will be classified as **an unexpected and related SAE**.

6.8 Reporting procedure to Research Ethics Committee (REC)

SAEs categorised by the CI as unexpected and related will be subject to expedited reporting to the REC by the Study Office within 15 days after the Study Office has been notified. A copy will also be sent to the University of Birmingham Research Governance Team at the same time.

The Study Office (on behalf of the CI) will inform all PIs of relevant information about SAEs that could adversely affect the safety of participants.

The REC will be notified immediately if a significant safety issue is identified during the course of the study. The University of Birmingham Research Governance Team will also be informed at the time that the REC is informed.

7 DATA ACCESS AND QUALITY ASSURANCE

7.1 Confidentiality of personal data

Individual participant information obtained as a result of this study is considered confidential. Each participant will be allocated a unique study number at recruitment.

Personal data and sensitive information required for ROCKeTS GEN V2 will be collected directly from study participants and hospital notes. Participants will be informed about the transfer of this information to University of Birmingham and asked for their consent. The data will be entered onto a secure computer database, either directly via the internet using secure socket layer encryption technology or indirectly from paper by ROCKeTS GEN V2 member of staff. Study database will be held in a secure internet facility (REDCap). REDCap (Research Electronic Data Capture) is a secure, web-based software platform designed to support data capture for research studies, providing 1) an intuitive interface for validated data capture; 2) audit trails for tracking data manipulation and export procedures; 3) automated export procedures for seamless data downloads to common statistical packages; and 4) procedures for data integration and interoperability with external sources. Data will be stored on a secure server under the provisions of the Data Protection Act and/or applicable laws and regulations. Access to data will be restricted by usernames and

passwords. The necessary study data will be encrypted. No study data will be held in handheld media, laptops, personal computers, or other similar media.

The online database will be maintained according to prescribed security policies of University of Birmingham. These cover assignment of passwords, encryption, database immediate back-up, offsite back-up and disaster recovery processes. Electronic data will be backed up every 24 hours to both local and remote media in encrypted format. Paper-based data (e.g. signed consent forms) or any paper based Case Report forms will be kept in locked filing cabinets.

Participants will also be informed that, and consent to, their samples, being transferred from local centres to the central laboratory. Samples will only be identified by study number. Central laboratory staff will not have access to personal data.

All personal information received in paper format for the study will be held securely and treated as strictly confidential according to University of Birmingham policies. All staff involved in the study (clinical and academic) share the same duty of care to prevent unauthorised disclosure of personal information. No data that could be used to identify an individual will be published.

7.2 Monitoring and audit

Investigators and their host Trusts will be required to permit study-related monitoring and audits to take place by the Study Office or Sponsor, providing direct access to source data and documents as requested. Trusts may also be subject to inspection by the Research and Development Manager of their own Trust and should do everything requested by the CI to prepare and contribute to any inspection or audit. Study participants will be made aware of the possibility of external audit of data they provide in the PIS.

7.3 Statistical monitoring throughout the study

The prevalence of OC in the study will be constantly monitored and sample size calculations will be reviewed to check if the study has accrued enough samples and data to report.

7.4 Long-term storage of data

After the end of the study, the site files from each centre should be archived by the NHS Trust as per regulations for a non-CTIMP.

All data will be stored for at least 10 years. Any queries or concerns about the data, conduct or conclusions of the study can also be resolved in this time.

Study data will be stored within the University of Birmingham under controlled conditions for at least 3 years after closure. Long-term offsite data archiving facilities will be considered for storage after this time. The University of Birmingham has standard processes for both hard copy and computer database legacy archiving.

